2.3.4 Rationale for Dose Selection

Eltrombopag 150mg orally once daily is selected as the starting dose based on safety and efficacy data from two prior studies conducted here at NIH. In a phase II (NCT00922883) trial with refractory SAA patients, EPAG proved to be efficacious without dose limiting toxicities at a dose of 150mg. Furthermore, no increased or unexpected toxicities were noted with Eltrombopag, CsA, and h-ATG combination (12-H-0150). Pharmacokinetics data indicate higher plasma drug concentrations with regular dose of EPAG in patients with East Asian and Southeast Asian ancestry, therefore, a starting dose of 75mg daily will be administered as in our previous protocols.

In our previous protocols, a starting dose of cyclosporine 3mg/kg twice a day is given (higher dose) with a target drug level between 200 and 400mcg/L. For this protocol, we plan to administer 2mg/kg/day (lower dose). CsA has been shown to work in SAA at varying doses, schedule, and therapeutic trough. However, dedicated dose escalation studies to guide CsA dosing are lacking. At the clinical center, initial starting dose of 6mg/kg/day has been prescribed historically whereas doses as high as 12mg/kg/day have been used in German trials [37]. Therapeutic goals have also varied among trials from different institutions, and in developing countries the dose is typically adjusted based on toxicities. Lower dose CsA is not studied previously as the starting dose but we have observed ongoing hematologic response and delay in relapses with prolonged administration of lower dose CsA after initial response [38]. Lower dose CsA resulted in suppression of cytotoxic T cells and increase in Tregs in patients with atopic dermatitis, another chronic autoimmune condition, suggesting a degree of immunosuppression with this dose [39].

Lower dose CsA is also safer to administer because of less toxicities and no requirements to follow levels, which may not be readily available in certain outpatient settings. Patients will only continue 2mg/kg until the initiation of standard therapy at CC, at which time the dose will be increased to standard 3mg/kg twice a day with a target goal between 200 and 400mcg/L to complete 6 months.

Abbreviated Title: Early Initiation of Oral Therapy for Naïve Severe Aplastic Anemia (SAA)

Version Date: 11/05/2025

After 6 months, CsA will be decreased to 2mg/kg for 18 months to complete 2 years as employed in 12-H-0150.

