5 TREATMENT PLAN

Patients will commence therapy with cyclosporine and eltrombopag as outpatients (if transfer to the Clinical Center is anticipated to require >72 hours or upon evaluation to the Clinical Center if <72 hours). Medications will be shipped to the patient at their provided address. After beginning cyclosporine and eltrombopag, monitoring blood work will be obtained at least weekly, more frequent if clinically indicated. For outpatients, a member of the NIH bone marrow failure team (research nurse, physician assistant, or physician) will speak by telephone with the patient or responsible family member every week, to ascertain symptoms and for any evidence of drug toxicity or intolerance (Appendix B). Within 8 weeks after consent, all subjects will have their evaluation at the Clinical Center except if grace period is granted in special circumstances (defined in Section 9.6) and receive the standard treatment with h-ATG, higher dose cyclosporine (3mg/kg twice a day), and eltrombopag daily after full work up is completed here. For patients without grace period extension, the evaluation will take place within 8 weeks of initiation of oral treatment but the administration of the standard treatment may not occur within the 8 weeks' time frame. If ANC <200 at the initial visit at NIH, treatment with all three drugs may be initiated without waiting for the cytogenetics.

If participants are unable to come to the NIH due to unanticipated reason beyond their control, the administration of the standard treatment with h-ATG, higher dose cyclosporine, and continuation of eltrombopag daily may be performed by subject's local physician/institution with guidance from the NIH bone marrow failure team after the full work up is completed as listed in section 6.1 (Clinical studies to be performed at the Clinical Center on first visit) and results reviewed by the NIH bone marrow failure team. If this is to occur, specialized studies (marked as * in section 6.1) may be omitted.

Abbreviated Title: Early Initiation of Oral Therapy for Naïve Severe Aplastic Anemia (SAA)

Version Date: 11/05/2025

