5.1 CYCLOSPORINE (CSA)

Day 1 of cyclosporine to Day 1 of admission for h-ATG:

For all subjects, cyclosporine will be started on day 1 at 2mg/kg/day by mouth administered daily at a fixed dose until Day 1 of h-ATG. Given low dose, cyclosporine therapeutic trough levels will only be checked per PI or local physician's discretion if concerning toxicity signs or symptoms. Cyclosporine dose may be interrupted or adjusted as clinically indicated at the discretion of the investigator for side effects. Interruptions or dose adjustments as a consequence of a serious adverse event will be included in the SAE Report.

Cyclosporine can result in many common side effects including headaches, nausea, gastrointestinal upset, hypertension, electrolyte imbalances and kidney injury. A complete list of adverse events can be found in section 12.4.2. Additionally, Appendix A will be sent to the outside physician to serve as a guiding document about drug administration, drug interactions (listed in section 5.11), dosage, adverse events, and monitoring. Our research team will be conducting weekly telephone follow up with patients +/- physicians to manage any side effects related to medications.

Day 1 of h-ATG to month 6 dosing:

For subjects \geq 12 years of age, cyclosporine will be increased to 3 mg/kg/dose by mouth administered every 12 hours (total daily dose of 6 mg/kg/day). Dosing will be based on actual body weight except in obese subjects. For obese subjects (defined as a body mass index > 35 in adult subjects [> 17 years of age, cyclosporine dosage will be based on an adjusted body weight that is calculated as the midpoint between the ideal body weight and actual body weight (see below for definition of ideal body weight). Pediatric patients (aged 17 and under) will dose on actual body weight for patients $< 125\%$ Ideal Body Weight (IBW). For those $> 125\%$ IBW, dosing will be based on adjusted ideal body weight (see below).

For subjects $<$ 12 years of age, cyclosporine will be increased to 6mg/kg/dose by mouth administered every 12 hours (total daily dose of 12 mg/kg/day). Patients aged 17 and under will dose on actual body weight for patients $< 125\%$ IBW. For those $> 125\%$ IBW, dosing will be based on adjusted ideal body weight.

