5.2 ELTROMBOPAG

Subjects will initiate EPAG at a starting daily dose as detailed in Table 3, according to age and ethnicity. Pediatric subjects between 12 and 17 years of age will receive the adult dose of 150 mg daily. Those between 6 and 11 will start at 75 mg, and children between 3 and 5 years of age will be started at 2.5 mg/kg (Table 1).

To adjust for the higher expected exposure in patients from East Asian and Southeast Asian ancestry, the starting dose for East Asian and Southeast Asian subjects between 12 and 85 years of age will be 75 mg once daily. For East Asian and Southeast Asian subjects between 6 and 11 years of age, the starting dose will be 37.5 mg once daily, and for children between 3 and 5, the starting dose will be 1.25 mg/kg (Table 3). EPAG will be administered orally as tablets or an oral suspension from sachet of EPAG powder. If an adult receives the oral suspension administration of EPAG, the required number of sachets will be used to administer the below adult doses. Detailed information about the supply and tablet/PfOS availability is in section 13.1.

Table 1. Dosing according to age and ethnicity

Age groups	Daily dose
Non-Asian	
12-85	150 mg
6-11	75 mg
3-5	2.5 mg/kg
East Asian, Southeast Asian	
12-85	75 mg
6-11	37.5 mg
3-5	1.25 mg/kg

EPAG may be taken on an empty stomach (1 hour before or 2 hours after a meal) or with food containing little (<50 mg) or preferably no calcium or dairy products. Allow at least a 4-hour interval between EPAG and other medications or products containing polyvalent cations (e.g. calcium, magnesium, aluminum, zinc, selenium or iron) such as antacids, dairy products, and mineral supplements to avoid significant (70-75%) reduction in eltrombopag absorption due to chelation.

EPAG dose may be interrupted when clinically indicated at the discretion of the investigator (for example if the patient is in the intensive care unit and unable to take PO medications).

Interruptions such as delays in request for medication refills or medication errors by subjects, or during circumstances such as COVID 19 pandemic that do not result in a serious adverse event or impact the integrity of the research data, will only be recorded in the medical record.

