5.10 INFECTION PROPHYLAXIS AND MONITORING

Pneumocystis jiroveci prophylaxis: During lower dose of CsA, routine *Pneumocystis jiroveci* prophylaxis (PJP) is not indicated. However, in patients with severe lymphopenia (Absolute lymphocyte counts <500/uL), PJP prophylaxis will be considered per PI discretion. It will be initiated upon starting h-ATG and higher dose of cyclosporine 3mg/kg q12h (6mg/kg q12h for pediatric) at the Clinical Center. Aerosolized pentamidine will be used as prophylaxis against *Pneumocystis jiroveci*, 300 mg approximately every 4 weeks by inhalation beginning the first month of higher cyclosporine therapy and to continue until month 6 when the cyclosporine dose is reduced.

Dapsone or another prophylactic regimen against *Pneumocystis jiroveci* may be substituted at the discretion of the PI. Bactrim (TMP/SULF) will be avoided because trimethoprim is a moderate to strong inhibitor of CYPs that may theoretically result in enhanced activity of EPAG. Children under 5 years of age (approximate) are often not able to complete the inhalation treatment with pentamidine and will receive dapsone or another prophylactic regimen at the discretion of the PI.

Antiviral prophylaxis: During lower dose of CsA, Valacyclovir is not indicated. However, in patients with severe lymphopenia (Absolute lymphocyte counts <500/uL), Valacyclovir prophylaxis will be considered per PI discretion. Valacyclovir, 500 mg once daily, will be administered for at least 1 month in all subjects regardless of HSV serology status at the time of h-ATG and higher dose cyclosporine at the Clinical Center. Pediatric subjects less than 40 kg will receive acyclovir (or equivalent) at 20mg/kg PO q12h to a maximum dose of 800mg q12h. Prophylaxis may be extended at the discretion of the PI.

Antibacterial and antifungal prophylaxis will not be included systematically with the immunosuppressive regimen but may be administered at the discretion of the PI or treating physician on a case-by-case basis.

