12 HUMAN SUBJECT PROTECTION

12.1 RATIONALE FOR SUBJECT SELECTION

The study will be open to all subjects who satisfy the inclusion criteria and provide an informed consent to the protocol. No subjects will be excluded from participation based on gender, race or ethnicity. We do not anticipate enrollment of NIH staff. This is a rare and debilitating disease. To our knowledge, currently, there are no NIH staff that would qualify for this study.

This study will be open to all patients who fit the inclusion criteria and provide informed consent to protocol participation. Epidemiologic studies suggest that the gender will be approximately evenly split between male and females, and that 90% of the patients will be Caucasian. However, previous experience at our institution suggests that distribution will be:

- By gender: 48% males and 52% females;
- By race/ethnicity: approximately 58% White, 20% Black, 10% Asian and 17% Hispanic;
- By age: will range between 3 and 82 (median age of 30) and roughly 20% of patients will be under the age of 18.

For subjects of Asian ethnicity: Plasma eltrombopag area under the curve was approximately 70% higher in East and Southeast Asian (ethnicity self-reported) subjects as compared to non-Asian subjects who were predominantly Caucasian. Therefore, subjects of Asian heritage will be included but they will be initiated at a lower dose and monitored closely as described in the treatment plan.

For subjects with renal impairment: The pharmacokinetics of eltrombopag has been studied in adult patients with renal impairment. Following administration of a single 50 mg dose, there was a trend for reduced plasma eltrombopag exposure in patients with renal impairment, but there was substantial variability and significant overlap in exposures between patients with renal impairment and healthy volunteers. Therefore, patients with impaired renal function will be included and given the protocol-defined dosages, but participation will be monitored closely.

For subjects with hepatic impairment: Pharmacokinetics of eltrombopag has been studied in adult patients with hepatic impairment. Following the administration of a single 50 mg dose, the $AUC_{0-\infty}$ of eltrombopag was increased by 41% in subjects with mild hepatic impairment and by

Abbreviated Title: Early Initiation of Oral Therapy for Naïve Severe Aplastic Anemia (SAA)

Version Date: 11/05/2025

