Doses for children between the ages 4 to 5 (2.5mg/kg non-East/South Asian participants, and 1.25mg/kg East/South Asian participants) will be provided in the form of sachets (when available). The powder for oral suspension is a reddish brown to yellow powder in a sachet. Two PfOS strengths are available, containing eltrombopag olamine equivalent to 12.5 mg and 25 mg of eltrombopag free acid. Reconstitution of eltrombopag PfOS will follow instructions outlined in the Investigator’s Brochure and Package Insert.

Stability: Store, both tablets and powder, at 25°C (77°F); excursions permitted to 15o to 30°C (59o to 86°F) [see *USP Controlled Room Temperature*].

Shipping: The NIH Investigational Drug Management and Research Section (IMDRS) will be responsible for receiving, storing, dispensing and accounting for drug product. The shipping address for Novartis supplied investigational agent is:

National Institutes of Health

[name]

[name]

Abbreviated Title: Early Initiation of Oral Therapy for Naïve Severe Aplastic Anemia (SAA)

Version Date: 11/05/2025

Accountability Procedures: Drug accountability records will be maintained for all clinical supplies. All empty and partially used vials and clinical trial supplies will be destroyed locally according to the institution's standard operating procedures for drug destruction. The pharmacy will maintain detailed documentation of the number and identification of vials, which are destroyed, and copies of these documents will be provided to the Sponsor and Novartis. Disposition of all unused boxes of study drug will be carried out according to instructions provided by the Sponsor and/or Novartis at the end of the study after drug accountability is performed.

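### Sections conflict twofold on starting dose in two places: which ancestry group gets reduced eltrombopag, and which ages get the higher cyclosporine dose with h-ATG

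*Combined protocol and SAP*

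**What the plan says.** **Eltrombopag, by ancestry.** Section 2.3.4 rests the reduced dose on "higher plasma drug concentrations with regular dose of EPAG in patients with East Asian and Southeast Asian ancestry". Section 5.2 agrees: "the starting dose for East Asian and Southeast Asian subjects between 12 and 85 years of age will be 75 mg once daily". Its table, and the one in Appendix A, have two row groups, one for East and Southeast Asian patients and one labelled Non-Asian. Section 13.1, on the powder for suspension, groups patients differently: "Doses for children between the ages 4 to 5 (2.5mg/kg non-East/South Asian participants, and 1.25mg/kg East/South Asian participants". Section 12.1 says that "subjects of Asian heritage will be included but they will be initiated at a lower dose"; the same sentence then refers to the treatment plan.

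**Cyclosporine from day 1 of h-ATG.** Section 5.1 gives 3 mg/kg every 12 hours from age 12 upward. For those under 12 it says "cyclosporine will be increased to 6mg/kg/dose by mouth administered every 12 hours (total daily dose of 12 mg/kg/day". Section 5.10 writes "higher dose of cyclosporine 3mg/kg q12h (6mg/kg q12h for pediatric", with no age limit attached to the last word. The Section 5 overview gives "higher dose cyclosporine (3mg/kg twice a day" for all subjects, and Section 2.3.4 likewise makes no age exception.

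**Youngest eltrombopag band.** It is 3 to 5 years in Section 5.2, 2 to 5 in Appendix A and 4 to 5 in Section 13.1. Eligibility starts at 3 years (Sections 4.1 and 12.2).

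**The concern.** Two readers of the same protocol could start the same patient on doses that differ by a factor of two, and each could cite a current section in support. That bears on safety first. It also bears on the uniformity of the regimen whose toxicity the trial measures: the primary endpoint counts treatment-related serious events during the oral phase, and Section 5.9 says that the eltrombopag-cyclosporine interaction potential is unknown. Eltrombopag is often shipped to patients and started away from the Clinical Center, and Appendix A, the local physician's guide, repeats the gap in the ancestry rows.

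**Working it through.** No sample-size, power or error-rate figure is involved. The check sets the dosing statements side by side and follows each kind of patient through them.

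**1. Eltrombopag ancestry group**

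| Place | Group given the reduced dose |
|---|---|
| 2.3.4; 5.2 text and table; Appendix A | East and Southeast Asian |
| 13.1 (ages 4 to 5) | East/South Asian |
| 12.1 | Asian heritage, then a reference to the treatment plan |

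- East Asian, any age: the reduced dose everywhere. No conflict.
- South Asian or other Asian: in neither row of the two tables. The text of 2.3.4 and 5.2 does not name them in the exception, 12.1 includes them by its wording, and 13.1 includes South Asian children aged 4 to 5.
- Southeast Asian, aged 4 to 5: reduced in 5.2, but outside the reduced group in 13.1 if that sentence is read literally.

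Size: 150/75 = 2.0 (age 12 and over), 75/37.5 = 2.0 (6 to 11) and 2.5/1.25 = 2.0 (youngest band). For a child of an assumed 15 kg: 2.5 × 15 = 37.5 mg against 1.25 × 15 = 18.75 mg daily.

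**2. Cyclosporine with h-ATG**

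Daily totals: 3 × 2 = 6 and 6 × 2 = 12 mg/kg/day. Both reproduce the totals printed in 5.1. Ratio 12/6 = 2.0.

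| Age | 5.1 | 5.10 | 2.3.4 and 5 |
|---|---|---|---|
| Under 12 | 12 mg/kg/day | 12 | 6 |
| 12 to 17 | 6 | 12, if pediatric means 17 and under | 6 |
| 18 and over | 6 | 6 | 6 |

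The reading of pediatric as 17 and under is the protocol's own: 5.1 attaches that age to the word in its body-weight rule, and 5.2 applies the word to adolescents: "Pediatric subjects between 12 and 17 years of age will receive the adult dose of 150 mg daily". For a 12- to 17-year-old of an assumed 50 kg, 6 × 50 = 300 mg against 12 × 50 = 600 mg per day, before any trough adjustment.

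**3. Youngest eltrombopag band**

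All three versions carry the same per-kg doses (2.5, or 1.25 if reduced), so the ratio is 1.0. Age 2 is ineligible. Age 3 is missing only from the 13.1 sentence on sachet supply and is dosed in 5.2.

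**4. Scale**

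- Asian share: 2/36 = 5.6% (Table 1 in Section 2.3.7) to 10% (Section 12.1).
- Under-18 share: 5/36 = 13.9% to about 20% (same sources).
- Section 9.3 counts 39 patients as already accrued, leaving 80 − 39 = 41. Among these: 0.056 × 41 = 2.3 to 0.10 × 41 = 4.1 Asian patients, and 0.139 × 41 = 5.7 to 0.20 × 41 = 8.2 under 18.

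These are ceilings on the groups within which a conflict can arise, not counts of affected patients. The South Asian share and the split of minors at age 12 are not given.

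**The case against.** The best defence is that the controlling sections can be identified and the others are incidental.

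- **Cyclosporine.** A schedule-of-events footnote sends the reader to 5.1 for the age-based increase, and 5.1 states its cut and daily totals explicitly. Section 5 is an overview and 5.10 concerns infection prophylaxis. Doses are then adjusted to a trough of 200 to 400 mcg/L, with weekly inpatient levels (5.1 and 6.3). This stands as mitigation. It does not remove the contradiction, because trough adjustment follows the first dose and does not define it.
- **Eltrombopag.** Section 13.1 is a supply section, and its group may simply be a slip for Southeast Asian. Sections 2.3.4 and 5.2 can be read as a general dose with one named exception, which would make Non-Asian a loose label. That is plausible but is inference, and deferring to 5.2 does not close a gap that lies in 5.2's own table.

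Four stronger readings are tempting and are not supported:

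- A reader might infer that the differing youngest bands give children different eltrombopag doses. They do not; the per-kg dose is the same in all three.
- Section 12.1 might be taken as a third dosing rule. Its sentence defers to the treatment plan, and the exposure figure before it (about 70% higher) is for East and Southeast Asian subjects.
- One might count all Asian and all under-18 patients among the 80 as affected. East Asian patients have no conflict, and different sections clash on either side of age 12.
- One might suppose that Appendix A spreads the cyclosporine conflict to local physicians. It lists only the 2 mg/kg daily dose, and it asks them to discuss changes with the investigators. Only the eltrombopag row gap appears there.

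**Conclusion.** The concern holds for two conflicts in the current text, each with a twofold difference in starting dose: the ancestry group for reduced eltrombopag, and the age rule for cyclosporine with h-ATG. The first is the less protected, since neither the schedule pointer nor trough adjustment applies to it. The second is real on paper but eased by both. The differing youngest eltrombopag band is a consistency correction only.

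The number of patients affected cannot be derived from the documents. It is some part of the 6% to 10% Asian and 14% to 20% under-18 shares, and for a change made now it falls mainly among the 41 extension patients. The conclusion assumes that pediatric in 5.10 carries the meaning that 5.1 gives it, and that 13.1 is read as printed. If both were drafting slips, the South Asian gap in the tables and the missing age exception in 2.3.4 and Section 5 would remain. Sample size, power and error rates are untouched. This should be corrected, as a drafting contradiction with a dosing consequence for few patients. No view is taken on which dose, group or age cut is right.

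**What to change.** The sponsor should reconcile Sections 2.3.4, 5, 5.1, 5.2, 5.10, 12.1 and 13.1 and Appendix A to one statement of ancestry groups and age bands per drug, so that every eligible patient falls in exactly one row. In practice:

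- use one set of ancestry terms throughout, with row labels that together cover all patients;
- replace the undefined word pediatric in 5.10 with an age or a reference to 5.1, and add the same reference to the overview statements in 2.3.4 and 5;
- align the youngest eltrombopag band with the eligibility age in all three places;
- reissue Appendix A to match.

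The content is the sponsor's decision. The cost is amendment wording and a corrected guide for local physicians; no design element, sample size or analysis changes.
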